8.7 EFFICACY DATA ENDPOINTS AND ANALYSES

8.7.1 Primary Efficacy Endpoint and Analyses

The clinical response to GKT137831 is defined as the percent change from baseline to Week 24 visit in serum GGT (primary efficacy endpoint).

Absolute serum GGT values as well as absolute change and percent change from baseline to Week 24 visit in serum GGT values will be provided at baseline and Week 24 visit for each allocated treatment group using summary statistics.

Due to the small sample size, the primary analysis will be conducted using a stepwise approach. The percent change from baseline to Week 24 visit in serum GGT will be analyzed using an Analysis of Covariance (ANCOVA) with the allocated treatment and disease severity at baseline as fixed effects, and the serum GGT baseline value as a continuous covariate.

The least square means estimate of the difference between each dose of GKT137831 and placebo alongside the 95% confidence interval will be calculated. Given two doses of GKT137831 are tested versus placebo, the 97.5% confidence interval of the least square mean of the difference between each dose of GKT137831 and placebo will also be calculated to account for the multiple testing using Hochberg adjustment.

If the normality assumption for the primary analysis is not met then the percent change from baseline in serum GGT at Week 24 will be analyzed non-parametrically through a stratified Wilcoxon Mann-Whitney (van Elteren) test. The normality assumption will be assessed through the examination of diagnostic residual plots.

The primary analysis will be performed using the ITT population and a sensitivity analysis will be done using the PP population. If the Wilcoxon Mann-Whitney test is used, a subgroup analysis for disease severity will also be performed.

8.7.2 Secondary and Tertiary Efficacy Endpoints and Analyses

Any analyses of the secondary and tertiary efficacy endpoints should be interpreted with care. The study has not been powered for the interpretation of these endpoints. Inferential statistical analyses performed on the secondary endpoints are included to aid interpretation and should not be considered as an alternative to the primary analysis for determining efficacy.

All the analyses on the secondary and tertiary efficacy endpoints will be performed on the ITT population.

The need for sensitivity analyses of the secondary endpoints on the PP population will be assessed after the blinded review of the major protocol deviations.

Secondary efficacy endpoints

The summaries and analyses planned for the secondary efficacy endpoints are described below.

Template Author: [name] Version 3.0 16AUG2017

• Absolute and percent change in serum GGT from baseline to each post-baseline assessment.

Absolute serum GGT values as well as absolute change and percent change from baseline in serum GGT will be provided at baseline and each post-baseline visit for each allocated treatment group using summary statistics.

The percent change from baseline to each post-baseline visit in serum GGT will be analyzed using a repeated measures ANCOVA model with the allocated treatment, the post-baseline visit and disease severity at baseline as fixed effects, the baseline serum GGT as a continuous covariate, and the interaction effect between treatment and visit.

Estimation will be performed using SAS[®] PROC MIXED with LSMEANS and REPEATED statement. An unstructured covariance matrix will be selected for the repeated measure analysis.

The least square means estimate of the percent change from baseline in serum GGT considered at each post baseline visit alongside its two-sided 95% CI and 97.5% CI will be presented as well as the associated standard error and the two-sided p-value.

Should the repeated measures analysis not converge or the normality assumption fail, data from each visit will be compared separately using the same method as the primary analysis.

• Absolute change in ELF score from baseline to Weeks 12 and 24 visits

Absolute ELF scores and absolute changes from baseline to Weeks 12 and 24 visits in ELF scores will be provided at baseline, Week 12 and Week 24 visits for each allocated treatment group using summary statistics.

The absolute change from baseline to Week 12 visit in ELF score will be analyzed using an ANCOVA with the allocated treatment and disease severity at baseline as fixed effects, and the baseline ELF score as a covariate.

The absolute change from baseline to Week 24 visit in ELF score will be analyzed similarly.

• Absolute and percent change in serum ALP from baseline to each post-baseline assessment.

Absolute serum ALP values as well as absolute change and percent change from baseline to each post-baseline assessment in serum ALP will be provided at baseline and each post-baseline visit for each allocated treatment group using summary statistics.

In addition, the proportion of subjects achieving a 15, 20, 30, and 40% reduction in serum ALP at each post-baseline visit will be tabulated for each allocated treatment group.

The percent change from baseline to each post-baseline visit in serum ALP will be analyzed using a repeated measures ANCOVA model with the allocated treatment, the post-baseline visit and disease severity at baseline as fixed effects, the baseline serum ALP as a continuous covariate, and the interaction effect between treatment and visit.

Estimation will be performed using SAS[®] PROC MIXED with LSMEANS and REPEATED statement. An unstructured covariance matrix will be selected for the repeated measure analysis.

The least square means estimate of the percent change from baseline in serum ALP considered at each post baseline visit alongside its two-sided 95% CI and 97.5% CI will be presented as well as the associated standard error and the two-sided p-value.

Should the repeated measures analysis not converge or the normality assumption fail, data from each visit will be compared separately using the same method as the primary analysis.

• Absolute and percent change in serum levels of hsCRP and fibrinogen from baseline to each post-baseline assessment.

Absolute serum levels of hsCRP as well as absolute change and percent change from baseline to each post-baseline assessment in serum levels of hsCRP will be provided at baseline and each post-baseline visit for each allocated treatment group using summary statistics.

The percent change from baseline to each post-baseline visit in serum level of hsCRP will be analyzed using a repeated measures ANCOVA model with the allocated treatment, the postbaseline visit and disease severity at baseline as fixed effects, the baseline serum level of hsCRP as a continuous covariate, and the interaction effect between treatment and visit.

Estimation will be performed using SAS[®] PROC MIXED with LSMEANS and REPEATED statement. An unstructured covariance matrix will be selected for the repeated measure analysis.

The least square means estimate of the percent change from baseline in serum level of hsCRP considered at each post baseline visit alongside its two-sided 95% CI and 97.5% CI will be presented as well as the associated standard error and the two-sided p-value.

Should the repeated measures analysis not converge or the normality assumption fail, data from each visit will be compared separately using the same method as the primary analysis.

Similar summary statistics will also be provided on absolute serum levels of fibrinogen as well as on absolute change and percent change from baseline to each post-baseline assessment.

The percent change from baseline to Week 24 visit in serum level of fibrinogen will be analyzed using an Analysis of Covariance (ANCOVA) with the allocated treatment and disease severity at baseline as fixed effects, and the baseline value of the serum level of fibrinogen as a continuous covariate.

• Absolute and percent change in serum ALT, AST, conjugated and total bilirubin from baseline to each post-baseline assessment.

Absolute serum ALT values as well as absolute change and percent change from baseline to each post-baseline assessment in serum ALT values will be provided at baseline and each post-baseline visit for each allocated treatment group using summary statistics.

The percent change from baseline to each post-baseline visit in serum ALT values will be analyzed using a repeated measures ANCOVA model with the allocated treatment, the postbaseline visit and disease severity at baseline as fixed effects, the baseline serum ALT value as a continuous covariate, and the interaction effect between treatment and visit.

Estimation will be performed using SAS[®] PROC MIXED with LSMEANS and REPEATED statement. An unstructured covariance matrix will be selected for the repeated measure analysis.

The least square means estimate of the percent change from baseline in serum ALT considered at each post baseline visit alongside its two-sided 95% CI and 97.5% CI will be presented as well as the associated standard error and the two-sided p-value.

Should the repeated measures analysis not converge or the normality assumption fail, data from each visit will be compared separately using the same method as the primary analysis.

Serum AST and serum level of total bilirubin will be summarized and analysed similarly.

Similar summary statistics will also be provided on absolute serum level of conjugated bilirubin as well as on absolute change and percent change from baseline to each post-baseline assessment.

The percent change from baseline to Week 24 visit in serum level of conjugated bilirubin will be analyzed using an Analysis of Covariance (ANCOVA) with the allocated treatment and disease severity at baseline as fixed effects, and the baseline value of the serum level of conjugated bilirubin as a continuous covariate.

• Absolute and percent change in the FIB-4 and APRI scores from baseline to each postbaseline assessment

Absolute FIB-4 scores as well as absolute change and percent change from baseline to each post-baseline assessment in FIB-4 scores will be provided at baseline and each post-baseline visit for each allocated treatment group using summary statistics.

The percent change from baseline to Week 24 visit in FIB-4 score will be analyzed using an Analysis of Covariance (ANCOVA) with the allocated treatment and disease severity at baseline as fixed effects, and the baseline value FIB-4 score of as a continuous covariate.

The APRI scores will be summarized and analysed similarly.

• Absolute and percent change in liver stiffness from baseline to Week 24 visit.

Only subjects with liver stiffness values at both baseline and Week 24 visits will be taken into account for the summaries and analyses.

Absolute liver stiffness values as well as absolute change and percent change from baseline to Week 24 visit in liver stiffness values will be provided at baseline and Week 24 visit for each allocated treatment group using summary statistics.

The percent change from baseline to Week 24 visit in liver stiffness will be analyzed using an ANCOVA with the allocated treatment and disease severity at baseline as fixed effects, and the baseline liver stiffness value as a continuous covariate.

• Absolute and percent change in serum levels of collagen fragments (ProC3, ProC5, C3M, C4M, and BGM) from baseline to Weeks 12 and 24 visits.

Absolute serum levels of collagen fragments and absolute changes from baseline to Week 12 and Week 24 visits in serum levels of collagen fragments will be provided at baseline, Week 12 and Week 24 visits for each allocated treatment group using summary statistics.

The percent change from baseline to Week 12 visit in serum level of collagen fragments will be analyzed using an ANCOVA with the allocated treatment and disease severity at baseline as fixed effects, and the baseline serum level of collagen fragments as a continuous covariate.

The percent change from baseline to Week 24 visit in serum level of collagen fragments will be analyzed similarly.

• Absolute change in Quality of Life scores (based on the 6 domains of the PBC-40 Questionnaire) and Pruritus score (based on Pruritus VAS) from baseline to Weeks 12 and 24 visits.

The PBC-40 questionnaire will be summarized by domain using the scoring described in the coded-PBC-40 document.

If data are missing from a domain (typically missed or duplicated answers), the whole domain should be discarded if <50% of the items are completed. If >50% of the items have responses then the median value for the completed items in the domain should be ascribed to the missing items.

For each of the 6 domains (symptoms, itch, fatigue, cognition, social, emotional), the total scores as well as the absolute and percent changes from baseline to Week 12 and Week 24 visits in the domain's total scores will be provided at baseline, Week 12 and Week 24 visits for each allocated treatment group using summary statistics.

The Pruritus scores will be summarized similarly.

Tertiary efficacy endpoints

The summaries and analyses planned for the tertiary efficacy endpoints are described below.

• Absolute and percent change in serum level of total bile acids from baseline to Weeks 12 and 24 visits.

Absolute serum level of total bile acids and absolute changes from baseline to Weeks 12 and 24 visits in serum level of total bile acids will be provided at baseline, Week 12 and Week 24 visits for each allocated treatment group using summary statistics.

The percent change from baseline to Week 12 visit in serum level of total bile acids will be analyzed using an ANCOVA with the allocated treatment and disease severity at baseline as fixed effects, and the baseline serum level of total bile acids as a covariate.

The percent change from baseline to Week 24 visit in serum level of total bile acids will be analyzed similarly.

- **Proportion of subjects who meet the definition of PBC responder** applying the following two criteria:
 - ALP < 1.67xULN
 - ALP < $1.67 \times ULN$, ALP reduction $\ge 15\%$, and total bilirubin < ULN (composite criterion)

For each of the two above PBC response criteria, the proportion of responders at Weeks 12 and 24 visits will be presented for each allocated treatment group.

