### 10.4.3.3 Second Efficacy Analysis

Any analyses of the secondary efficacy endpoints should be interpreted with care. The study has not been powered for the interpretation of these endpoints. Inferential statistical analyses performed on the secondary endpoints are included to aid interpretation and should not be considered as an alternative to the primary analysis for determining efficacy. All analyses will be performed using the ITT population. Sensitivity analyses using the PP population may also be performed on secondary endpoints; these will be specified in the SAP.

The difference in the percent change from baseline in serum GGT between each dose level of GKT137831 and placebo will be estimated for all scheduled visits using a repeated measures analysis of covariance model with treatment, visit and disease severity as fixed effects, the baseline value as a continuous covariate and the interaction effect between treatment and visit. Should the repeated measures analysis not converge or the normality assumption fail, data from each visit will be compared individually using the same method as the primary analysis.

Protocol No.: GSN000300	Compound No.: GKT137831
Protocol Version No.: Final 4.0; Amendment 3	Sponsor: Genkyotex
Protocol Date: 24 July 2018	Author: Cmed Clinical Services

Descriptive summary statistics by treatment group and visit will be presented for the change from baseline and absolute values of ELF score. The difference in the change from baseline in ELF score between each dose level of GKT137831 and placebo will be estimated for all scheduled visits using the same methodology as for serum GGT.

Serum ALP will be summarized in the same way and analyzed using the same methodology as for serum GGT.

In addition the proportion of subjects achieving a 15, 20, 30, and 40% reduction in serum ALP will be tabulated.

Summary statistics will also be presented for the percent change from baseline, change from baseline and absolute values for all continuous secondary efficacy endpoints. The change from baseline in liver function tests other than ALP may also be analyzed in an exploratory manner using the same statistical methodology as for the serum GGT.

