6.4 VISIT WINDOWING

Visit windowing will be considered only for efficacy and pharmacodynamic assessments.

The halfway point corresponding to the visits will be considered in relation to the date of first dose. Efficacy assessments are planned to be conducted at Week 2, Week 6, Week 12, Week 18, Week 24 and Week 28 visits. The following windowing rules will be taken into account to establish the visit corresponding to each efficacy and pharmacodynamic assessment:

- Week 2: any efficacy or pharmacodynamic assessment performed between 2 to 28 days after the first dose;
- Week 6: any efficacy or pharmacodynamic assessment performed between 29 days to 63 days after the first dose;
- Week 12: any efficacy or pharmacodynamic assessment performed between 64 days to 105 days after the first dose;
- Week 18: any efficacy or pharmacodynamic assessment performed between 106 days to 147 days after the first dose;
- Week 24: any efficacy or pharmacodynamic assessment performed between 148 days to 182 days after the first dose;
- Week 28: any efficacy or pharmacodynamic assessment performed between 183 days to 203 days after the first dose;

If two (or more) assessments are recorded within a visit window, the closer (closest) to the halfway point will be taken into account for the analyses. If two assessments within a visit window are the same number of days from the halfway point, the second one will be taken into account for the summaries assuming that it is more reliable than the first one.

No programmatic windowing of visits will be considered for safety data. Post-baseline data will be presented according to the visit at which it was collected on the eCRF or as described in this SAP.

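### The repeated-measures models hold the baseline slope constant over visits; a baseline-by-visit term would guard against a modest loss of Week 24 precision in six supportive analyses, at negligible cost

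*SAP*

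**What the plan says.** SAP 8.7.2 models percent change in GGT at all post-baseline visits with treatment, visit and baseline disease severity as fixed effects, plus "the baseline serum GGT as a continuous covariate, and the interaction effect between treatment and visit". On the covariance it says: "An unstructured covariance matrix will be selected for the repeated measure analysis". ALP has the same form, with "the baseline serum ALP as a continuous covariate, and the interaction effect between treatment and visit", and the text is repeated for hsCRP and ALT. For the last two markers: "Serum AST and serum level of total bilirubin will be summarized and analysed similarly". Protocol 10.4.3.3 gives the GGT model as including "the baseline value as a continuous covariate and the interaction effect between treatment and visit" and applies it to ALP. Neither document has a baseline-by-visit term.

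The visits covered are set in SAP 6.4: "Efficacy assessments are planned to be conducted at Week 2, Week 6, Week 12, Week 18, Week 24 and Week 28 visits". Week 28 is four weeks after treatment ends.

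The primary analysis (SAP 8.7.1) is a single-visit Week 24 ANCOVA with treatment, severity "and the serum GGT baseline value as a continuous covariate", so its baseline slope belongs to Week 24 alone. If the repeated-measures model does not converge or normality fails, "data from each visit will be compared separately using the same method as the primary analysis". When that method is ANCOVA, each visit again has its own slope.

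**The concern.** The model lets the treatment effect and the covariance differ freely by visit but holds the baseline slope constant. If percent change depends on baseline more strongly at Week 24 than at Week 2, the fitted common slope falls below the Week 24 slope. It falls furthest when early visits are less variable, because they then carry more weight. Part of the baseline-explained variation at Week 24 stays in the residual, and the interval is wider than it need be. If the association instead weakens over time, the common slope over-adjusts, which also loses some precision.

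For GGT little depends on this, because the primary ANCOVA already supplies a freely adjusted Week 24 result. For ALP, hsCRP, ALT, AST and total bilirubin, the repeated-measures model is the only planned inference at Week 24 unless the fallback is triggered. The model estimates for ALP, hsCRP and ALT are among the top-line tables in SAP Appendix 1.

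**Working it through.** **Inputs from the documents.** 34 per arm, SD 30 (active) and 40 (placebo), a 28-point difference and two-sided alpha 0.023475 (SAP 5.4); visits from SAP 6.4. **Assumed, because the documents give none:** the within-arm correlation r of baseline with percent change at Week 24, how it changes over visits, the between-visit correlation, and the SD at visits before Week 24.

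**Scale check.** The root-mean-square SD is √((30² + 40²)/2) = 35.36. With the 3/π efficiency of the Wilcoxon test, the effective n is 34 × 3/π = 32.47. The SE is √((900 + 1600)/32.47) = 8.77, and 28/8.77 = 3.19. The Welch noncentral t then gives 80.4% power (79.6% by simulated Mann-Whitney tests). The stated 80% reproduces, so these SDs are a fair scale.

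**Large-sample formula.** Let b be the vector of visit-specific slopes per SD of baseline and S the residual covariance. The common slope is c = (1′S⁻¹b)/(1′S⁻¹1). The Week 24 half-width with baseline-by-visit, relative to one slope, is √(s24² / (s24² + (b24 − c)²)).

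Example with r = 0.3, five on-treatment visits, linear growth and AR correlation 0.8: b24 = 0.3 × 35.36 = 10.61, s24 = 35.36 × √0.91 = 33.73, s24² = 1137.7.

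- Equal SDs: c = 0.57 × b24, so b24 − c = 4.56. The ratio is √(1137.7/(1137.7 + 20.8)) = 0.991, or 0.9% narrower.
- SD rising from 45% of its Week 24 value: c = 0.07 × b24, so b24 − c = 9.87. The ratio is √(1137.7/(1137.7 + 97.4)) = 0.960, or 4.0% narrower.

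While c lies between 0 and b24, the gain cannot exceed 1 − √(1 − r²): 2.0% at r = 0.2, 4.6% at 0.3 and 13.4% at 0.5.

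**Finite-sample simulation.** REML, unstructured covariance, N = 102, complete data, 120 to 150 trials per scenario. Entries are Week 24 95% half-widths for BID versus placebo, in percentage points.

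| Growth of slope; SD pattern | r | One slope | By visit | Change |
|---|---|---|---|---|
| Linear; equal | 0.3 | 16.25 | 16.13 | −0.7% |
| Linear; equal | 0.5 | 15.13 | 14.82 | −2.0% |
| Late; rising from 63% | 0.2 | 16.74 | 16.53 | −1.3% |
| Linear; rising from 63% | 0.3 | 16.66 | 16.24 | −2.5% |
| Late; rising from 63% | 0.3 | 16.86 | 16.40 | −2.7% |
| Linear; rising from 63% | 0.5 | 15.77 | 14.67 | −7.0% |
| Late; rising from 63% | 0.5 | 15.98 | 14.71 | −8.0% |
| Slope equal at all visits, or zero | | | | +0.1 to +0.2% |

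Across the growth scenarios the interval was narrower in 53–76% of trials at r = 0.2, 77–94% at r = 0.3 and 88–100% at r = 0.5. With equal slopes it was wider in 75–89% of trials. In the first row, the single-visit Week 24 ANCOVA gave 16.15 against 16.13 for the by-visit model. A large-sample extreme (r = 0.5, late growth, SD rising from 45%, exchangeable correlation 0.6) reaches about 17%.

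**Sensitivity to the early visits.** Large-sample reduction in the Week 24 SE, with correlation −0.30 at Week 24, AR 0.75 and six visits:

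| Correlation at Week 2 | SD rising 20 to 38 | Equal SDs |
|---|---|---|
| 0 | 3.2% | 0.9% |
| −0.15 | 1.8% | 0.25% |

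**Bias and error rate.** The complete-data simulations showed no systematic shift in the treatment estimate under either model. In separate simulations with missing-at-random dropout, rejection at the nominal 5% level was 4–6% under both.

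**The case against.** The strongest objection is that the growing association is assumed and the documents partly point the other way. Baseline enters percent change at every visit, so regression to the mean can act from Week 2. Protocol 2.1.3.1 describes GGT as responding within weeks, and SAP 6.2 treats liver-test reductions as nearly complete by Week 12. Both suggest an association that is present early. This stands, and it is why the larger gains should not be expected. It does not remove the point: Weeks 2 and 6 still share the slope with Week 24, and the term costs almost nothing if it proves unnecessary.

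A reader might also infer more than the documents support:

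- *That the fix is free.* It is not quite: intervals widen slightly when the slopes are equal.
- *That the Week 24 estimates are biased or the tests invalid.* Nothing in the documents or the simulations shows this.
- *That the two Week 24 GGT results in the top-line tables contradict each other.* They come from different adjustments and need not coincide even with complete data. SAP 8.7.2 says that the secondary analyses are not a substitute for the primary one, so a difference is not a defect.
- *That a gain near 8% is typical.* It needs several unfavourable assumptions at once, none of them supported by a figure in the documents.

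**Conclusion.** The point holds as an inexpensive improvement. Six repeated-measures models force one baseline slope on all visits, unlike the primary ANCOVA. If the baseline association grows towards Week 24, those models under-adjust at that visit. The avoidable width is about 0 to 3% of the half-width in most growth scenarios; on a half-width of about 16.7 points, 3% is 0.5 points. It reaches about 8% in simulation only with r near 0.5, an early association near zero and early visits much less variable. The effect is on precision in analyses the SAP calls unpowered and supportive, and the primary GGT result does not change.

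These sizes rest on assumed correlations and SD profiles, and the half-widths in the simulation table on complete data. The SAP's LOCF rule for Week 24-defined secondary endpoints was not modelled.

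**What to change.** Before unblinding, add a baseline-by-visit interaction to each of the six repeated-measures models in SAP 8.7.2 (GGT, ALP, hsCRP, ALT, AST, total bilirubin). List it in SAP section 10 as a change from protocol 10.4.3.3, so that the two documents do not conflict without explanation. Leave the covariance structure and the fallback as they are.

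The cost is one model term. With six post-baseline visits it adds 5 parameters per model, from about 100 subjects. It needs no new data or patients.

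Disease-severity-by-visit is optional. It is needed only if the Week 24 GGT estimate is meant to reproduce the primary ANCOVA with complete data, and it adds 5 more parameters (10 in total). It was not simulated. SAP section 9 allows for very few subjects having a baseline GGT below 2.5 × ULN; if so, omit this second term.

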5.4 SAMPLE SIZE JUSTIFICATION

A sample size of 34 randomly allocated and treated subjects within each treatment group with an overall sample size of 102 subjects will have 80% power to detect a 28% difference in the means of the percent change from baseline in serum GGT. A Wilcoxon Mann-Whitney test has been used for the sample size estimate because this represents the worst-case scenario with regards to the statistical power. A standard deviation of 30 for the active GKT137831 group and a standard deviation of 40 for the placebo group have been assumed based on a recent phase 3 clinical trial of OCA [1].

An overall two-sided Type I error of 5% has been considered for the sample size calculation. The Hochberg method will be used to adjust the alpha level for multiple comparisons. Therefore, the first dose level comparison at the final analysis will be tested against an alpha level of 0.04695 and the second dose level will be tested against an alpha level of 0.023475. The alpha level of 0.023475 has been used for the sample size calculation.

The sample size calculation assumes all subjects (including withdrawals) will be included in the analysis. As a result, there has been no adjustment for dropouts.

6 Statistical Considerations

The SAS system version 9.4 (or higher), will be used for all analysis, unless otherwise specified.

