6.2 MISSING DATA HANDLING

In the event of missing data at Week 24 visit for efficacy endpoints (see the list below), the Last Observation Carried Forward (LOCF) method will be applied by imputing Week 24 visit data with the last non-missing post-baseline data available at Week 12 visit (or at a later visit). If there is no non-missing post-baseline data or if the last non-missing post-baseline data is available at an earlier visit than Week 12 visit then the LOCF method will not be applied and no data will be imputed at Week 24 visit. Accordingly, the LOCF method will not be used for the interim analysis. The above-described use of the LOCF method for the imputation of missing data at Week 24 visit is based on recently published studies that have shown that the reductions in liver function tests are close to maximal effects after 12 weeks of treatment [2].

The LOCF method will be applied for the following efficacy endpoints:

- Primary efficacy endpoint;
- Week 24-defined secondary efficacy endpoints (except those defined for ELF and liver stiffness);
- Week 24-defined tertiary efficacy endpoint for total bile acids;
- Week 24-defined exploratory efficacy endpoints (except those from the assessments of the metabolomics signatures and additional biomarkers of interest)

The complete case approach will be applied for the analysis of categorical variables using a worst-case imputation strategy.

For all other analyses and summaries, no imputation will be performed other than to complete partial dates using standard imputation techniques as described below.

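### For ELF only, the SAP replaces the protocol's repeated-measures model with separate per-visit ANCOVAs and does not declare the change

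*SAP*

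**What the plan says.** Protocol section 10.4.3.3 states: "The difference in the change from baseline in ELF score between each dose level of GKT137831 and placebo will be estimated for all scheduled visits". The same sentence assigns ELF the serum GGT methodology. For GGT, that section specifies a repeated-measures ANCOVA with treatment, visit, disease severity, baseline value and treatment-by-visit interaction. Visits are compared one at a time only if that model fails to converge or normality fails.

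SAP section 8.7.2 keeps this model for GGT, ALP, hsCRP, ALT, AST and total bilirubin, with an unstructured covariance matrix. For ELF it says: "The absolute change from baseline to Week 12 visit in ELF score will be analyzed using an ANCOVA with the allocated treatment", with disease severity and baseline ELF also in the model, and it repeats the same analysis separately at Week 24. The ELF paragraphs contain no repeated-measures model and no fallback rule.

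SAP section 6.2 carries the last observation forward to Week 24 for the Week 24 secondary endpoints, "except those defined for ELF and liver stiffness", and allows no other imputation of values for ELF. SAP section 10, which records changes to the planned analyses, lists only the two-stage final analysis.

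**The concern.** The SAP makes the protocol's conditional fallback the default for one endpoint, without giving a reason or declaring it. The choice has a statistical consequence. Without imputation, the Week 24 ANCOVA uses only subjects with a Week 24 ELF value. The repeated-measures model would also use the Week 12 values of subjects who then miss Week 24, through the correlation between visits. It therefore gives a somewhat more precise Week 24 estimate, and one that remains valid if drop-out depends on the observed Week 12 value (missing at random).

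Missing Week 24 values are foreseeable. Protocol section 5.6.4 makes withdrawal compulsory for several reasons, some of them liver-related. ELF also matters to the secondary reading: Protocol section 2.1.3.2 presents anti-fibrotic activity as an important aim and regards ELF as suitable for assessing it.

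**Working it through.** **1. The plan's own figure.** The only sizing figure is for GGT. Inputs, all from SAP section 5.4: two-sided alpha 0.023475, power 80%, difference 28, SDs 30 and 40, Wilcoxon Mann-Whitney test.

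- Pooled SD = sqrt((30² + 40²)/2) = 35.36.
- n per arm = 2 × [35.36 × (z for alpha + z for power)/28]² = 30.79.
- Dividing by the Wilcoxon efficiency 3/π gives 32.24, so 33 per arm.
- Simulated Wilcoxon power at 34 per arm (20,000 runs) is 79.9%.

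The stated 34 per arm reproduces. It concerns GGT; all it contributes here is the arm size.

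**2. Precision at Week 24.** Let d be the share of subjects with ELF at Week 12 but not Week 24, and ρ the residual correlation between the two visits. The documents give neither, so both are assumptions: d = 5-20%, ρ = 0.3-0.8. With two visits and monotone missingness:

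- Var(repeated measures)/Var(per-visit ANCOVA) = 1 − dρ²
- Increase in standard error from the per-visit ANCOVA = 1/sqrt(1 − dρ²) − 1

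| d | ρ = 0.3 | ρ = 0.5 | ρ = 0.7 | ρ = 0.8 |
|---|---|---|---|---|
| 5% | 0.2% | 0.6% | 1.2% | 1.6% |
| 10% | 0.5% | 1.3% | 2.5% | 3.4% |
| 15% | 0.7% | 1.9% | 3.9% | 5.2% |
| 20% | 0.9% | 2.6% | 5.3% | 7.1% |

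Worked case: d = 10%, ρ = 0.7 gives 1 − 0.10 × 0.49 = 0.951, and 1/sqrt(0.951) − 1 = 2.5%. If all 34 per arm have Week 12 data, 34 × 0.90 = 30.6 enter the Week 24 ANCOVA. The repeated-measures model is worth 30.6/0.951 = 32.2, a gain of about 1.6 subjects per arm.

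**3. Bias at Week 24.** Simulation with 200,000 subjects per arm and no treatment effect. Drop-out after Week 12 followed a logistic function of the Week 12 value (slope 1 or 2 per SD, the same in both arms), calibrated to the stated rates. The table shows the absolute bias of the complete-case Week 24 difference in SD units, slope 1 / slope 2:

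| Drop-out by arm | ρ = 0.5 | ρ = 0.7 | ρ = 0.8 |
|---|---|---|---|
| 10% / 10% | 0.003 / 0.000 | 0.006 / 0.001 | 0.003 / 0.006 |
| 15% / 5% | 0.044 / 0.060 | 0.068 / 0.086 | 0.067 / 0.100 |
| 20% / 5% | 0.064 / 0.092 | 0.091 / 0.123 | 0.104 / 0.148 |
| 20% / 10% | 0.044 / 0.058 | 0.055 / 0.080 | 0.066 / 0.095 |

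The balanced row is zero within simulation error. A correctly specified repeated-measures likelihood model is consistent under this mechanism.

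**4. Who counts in d.** Early-termination visits include ELF sampling (Protocol section 7.5). Under SAP section 6.4, a sample on days 148-182 is assigned to Week 24, so that subject is not missing. Subjects who leave before the Week 12 window have no Week 12 value to contribute. A sample on days 106-147 is assigned to Week 18, where no ELF analysis is planned; neither model uses it. The relevant d is thus narrower than total drop-out.

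**The case against.** The strongest defence is that per-visit ANCOVA is a sound method and the protocol's own fallback. It also lets the baseline and stratum effects differ by visit, whereas the protocol's model as written holds them constant. Secondary analyses are unpowered and meant only to aid interpretation (Protocol section 10.4.3.3, SAP section 8.7.2), and the precision loss is small. All of this stands, and it limits the weight of the point. It does not explain an undeclared departure, and a baseline-by-visit term answers the modelling point for the baseline effect.

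A reader might infer more than the documents support:

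- **That ELF is the lead fibrosis endpoint.** It is the first fibrosis measure in the secondary list, but no hierarchy is stated and the SAP's Top Line table list contains no ELF table.
- **That Week 12 data are thrown away.** They enter the Week 12 ANCOVA and are lost only to the Week 24 estimate.
- **That leaving ELF unimputed is itself a departure.** Protocol section 10.4.3.7 confines imputation to the primary analysis and categorical variables. The departure is the model.
- **That collagen fragments and total bile acids need the same correction.** The protocol assigns them no repeated-measures model, and SAP section 6.2 already carries their Week 12 values forward.
- **That the SAP's analysis is biased in general.** In the simulated cases, bias needed drop-out that was both unequal between arms and dependent on Week 12 ELF.

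**Conclusion.** The discrepancy is confirmed for ELF: the protocol prescribes a repeated-measures ANCOVA, while the SAP substitutes two separate ANCOVAs and does not list the change. The cost is a Week 24 standard error about 0.2-7% larger, assuming d of 5-20% and ρ of 0.3-0.8. Bias is near zero with balanced drop-out and about 0.04-0.15 SD under unequal drop-out that depends on the Week 12 value. The bias figures rest on the assumed drop-out rates and on a common dependence in both arms. Protection from the repeated-measures model rests on data missing at random and a correctly specified model. This is a minor secondary-endpoint correction with no effect on the primary result.

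**What to change.** In SAP section 8.7.2, replace the two ELF ANCOVAs with one repeated-measures ANCOVA of the absolute change at Weeks 12 and 24. Include treatment, visit, treatment-by-visit, disease-severity stratum and baseline ELF, with unstructured covariance and, optionally, baseline-by-visit. Report the treatment difference at each visit. Keep the per-visit ANCOVA as the protocol's fallback if the model does not converge or normality fails. Using the SAP's GGT fallback sentence would also bring in the non-parametric step that the ELF text now lacks. Leave collagen fragments and total bile acids as they are.

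The cost is one paragraph of SAP text. The GGT code can be reused with two visits, and no new data are needed. If the sponsor prefers the per-visit ANCOVA as the default, SAP section 10 should declare it and give the reason before the final unblinding.
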